6 DOSING DELAYS/DOSE MODIFICATIONS

Dose delays for nivolumab and ipilimumab for adverse events are described below. There are no dose reductions of nivolumab or ipilimumab allowed. See section 5.6 for guidelines regarding resumption of nivolumab and ipilimumab following dose delays.

Please refer to the Nivolumab Investigator Brochure, Ipilimumab Investigator Brochure or Appendix B to the protocol for toxicity management algorithms which include specific treatment guidelines. These algorithms should be followed unless there are specific clinical circumstances which the treating physician indicates variations or alternative treatment is needed.

Evaluation of possible AEs should occur early, with early withholding of drug, and appropriate treatment as indicated in the management tables and following event specific guidelines. In some cases, nivolumab and ipilimumab may be resumed as per section 5.6

| ALL OTHER EVENTS* | Management/Next Dose for Nivolumab and combination Nivolumab/ipilimumab |
|---------------------------------|--|
| ≤ Grade 1 | No change in dose |
| Grade 2 | Hold until ≤ Grade 1 OR baseline (exceptions as noted below); Evaluate and continue at investigator discretion |
| Grade 3 | Off protocol therapy (exceptions as noted below) |
| Grade 4 | Off protocol therapy |

* **Not agent related**, or agent related non-immunologically mediated

Recommended management: As clinically indicated

| ALL OTHER EVENTS** | Management/Next Dose for Nivolumab and combination Nivolumab/ipilimumab |
|----------------------------------|---|
| ≤ Grade 1 | No change in dose |
| Grade 2 | Hold until ≤ Grade 1 OR baseline* When resolved < or following steroids resume at same dose level . |
| Grade 3 | Off protocol therapy (exceptions noted in 5.4) |

| ALL OTHER EVENTS* | Management/Next Dose for Nivolumab and combination Nivolumab/ipilimumab |
|---|--|
| Grade 4 | Off protocol therapy |
| ** immunologically mediated | |
| Recommended management: As clinically indicated | |

- Any grade 2 drug-related uveitis or eye pain or blurred vision that does not respond to topical therapy and does not improve to Grade 1 severity within the re-treatment period OR requires systemic treatment should go off protocol treatment.
- Any adverse event, laboratory abnormality, or intercurrent illness which, in the judgment of the investigator, presents a substantial clinical risk to the subject with continued study drug dosing should go off protocol treatment.
- Tumor pain or associated tumor flare does not require permanent discontinuation.
- Any grade < 2 laboratory only abnormality may continue study treatment at the discretion of the investigator. Any grade 3 or 4 drug-related laboratory abnormality or electrolyte abnormality, that can be managed independently from underlying organ pathology with electrolyte replacement, hormone replacement, insulin, or that does not require treatment **does not** require discontinuation.

| Skin Rash and Oral Lesions | Management/Next Dose for Nivolumab and combination Nivolumab/ipilimumab |
|--|--|
| ≤ Grade 1 | No change in dose;* evaluate and continue at investigator discretion |
| Grade 2 | Hold* until 1≤ Grade resolved^. Evaluate and continue at investigator discretion. |
| Grade 3 | Hold* until ≤ Grade 1; evaluate and resume at investigator discretion same dose level. |
| Grade 4 | Off protocol therapy |

*Patients with purpuric or bullous lesions must be evaluated for vasculitis, Steven-Johnson syndrome, TEN, and autoimmune bullous disease including oral lesions of bullous pemphigus/pemphagoid. Pruritus may occur with or without skin rash and should be treated symptomatically if there is no associated liver or GI toxicity. Note skin rash typically occurs early and may be followed by additional events particularly during steroids tapering.

Recommended management: AE management guidelines – Appendix B

| Liver Function AST, ALT, and Bilirubin (total) | Management/Next Dose for Nivolumab and combination Nivolumab/ipilimumab |
|--|---|
| ≤ Grade 1 | Hold pending evaluation. Continue treatment at same level at investigator decision. |
| Grade 2 | Hold until UNL or baseline. Evaluate and resume at investigator discretion same dose level. |
| Grade 3 | Off protocol therapy |
| Grade 4 | Off protocol therapy |

Continued treatment of active immune mediated hepatitis may exacerbate ongoing inflammation. Holding drug to evaluate LFT changes and early treatment are recommended.

| Liver Function AST, ALT, and Bilirubin (total) | Management/Next Dose for Nivolumab and combination Nivolumab/ipilimumab |
|---|--|
| LFT changes may occur during steroid tapers from other events and may occur together with other GI events including cholecystitis/pancreatitis. | |
| Recommended management: see Hepatic AE management algorithm | |

| Diarrhea/ Colitis | Management/Next Dose for Nivolumab and combination Nivolumab/ipilimumab |
|--|---|
| ≤ Grade 1 | Evaluate and continue treatment at same level at investigator discretion. |
| Grade 2 | Hold until Grade ≤1 or baseline following treatment algorithm; evaluate and resume at investigator discretion if additional therapy is not required. |
| Grade 3 | Hold until Grade ≤1 or baseline following treatment algorithm; evaluate and resume at investigator discretion. |
| Grade 4 | Off protocol therapy |
| See GI AE Algorithm for management of symptomatic colitis. Patients with grade 2 symptoms but normal colonoscopy and biopsies may be retreated after resolution. Please evaluate pituitary function prior to starting steroids if possible without compromising acute care. Evaluation for all patients for additional causes includes C. diff , acute and self-limited infectious and foodborne illness, ischemic bowel, diverticulitis, and IBD. | |
| Recommended management: see GI AE management Algorithm | |

| Pancreatitis Amylase/Lipase | Management/Next Dose for Nivolumab and combination Nivolumab/ipilimumab |
|--|---|
| ≤ Grade 1 | Continue treatment at same level at investigator discretion. |
| Grade 2 | Continue treatment at same level at investigator discretion if asymptomatic. |
| Grade 3 | Hold until Grade ≤2 . Resume at same dose level if asymptomatic. Patients who develop symptomatic pancreatitis or DM should be taken off treatment. |
| Grade 4 | Hold until Grade ≤2 . Resume at same dose level if asymptomatic. Patients who develop symptomatic pancreatitis or DM should be taken off treatment. |
| Patients may develop symptomatic and radiologic evidence of pancreatitis as well as DM and DKA. Lipase elevation may occur during the period of steroid withdrawal and with other immune mediated events or associated with colitis, hepatitis, and patients who have asymptomatic lipase elevation typically have self-limited course and may be retreated. For treatment management of symptomatic pancreatitis please follow the Hepatic Adverse Event Management Algorithm. | |

| Pneumonitis | Management/Next Dose for Nivolumab and combination Nivolumab/ipilimumab |
|--|---|
| ≤ Grade 1 | Hold dose pending evaluation and resolution to baseline including baseline pO ₂ . Resume no change in dose after pulmonary and/or ID consultation excludes agent associated lymphocytic pneumonitis. |
| Grade 2 | Hold dose pending evaluation. Resume no change in dose after pulmonary and/or ID consultation excludes nivolumab/ipilimumab associated lymphocytic pneumonitis As the cause of the pneumonitis. Off study if steroids are required. |
| Grade 3 | Hold dose pending evaluation. Resume no change in dose after pulmonary and/or ID consultation excludes nivolumab/ipilimumab associated lymphocytic pneumonitis as the cause of the pneumonitis. Off study if steroids are required. |
| Grade 4 | Off protocol therapy |
| Distinguishing inflammatory pneumonitis is often a diagnosis of exclusion for patients who do not respond to antibiotics and have no causal organism identified including influenza. Most patients with respiratory failure or hypoxia will be treated with steroids. Bronchoscopy may be required and analysis of lavage fluid for lymphocytic predominance may be helpful. Patients with new lung nodules should be evaluated for sarcoid like granuloma. Please consider recommending seasonal influenza killed vaccine for all patients. | |
| Recommended management: See Pulmonary Adverse Event Management Algorithm | |

| Other GI N-V | Management/Next Dose for Nivolumab and combination Nivolumab/ipilimumab |
|---|---|
| ≤ Grade 1 | No change in dose. |
| Grade 2 | Hold pending evaluation for gastritis duodenitis and other immune adverse events or other causes. Resume at investigator discretion. |
| Grade 3 | Hold pending evaluation until ≤ Grade 2. Resume at same dose level. If symptoms do not resolve within 7 days with symptomatic treatment patients should go off protocol therapy |
| Grade 4 | Off protocol therapy |
| Patients with grade 2 or 3 N-V should be evaluated for upper GI inflammation and other immune related events. | |

| Fatigue | Management/Next Dose for Nivolumab and combination Nivolumab/ipilimumab |
|---|--|
| ≤ Grade 1 | No change in dose. |
| Grade 2 | No change in dose |
| Grade 3 | Hold until ≤ Grade 2. Resume at same dose level at investigator discretion. |
| Grade 4 | Off protocol therapy |
| Fatigue is the most common adverse event associated with immune checkpoint therapy. Grade 2 or greater fatigue should be evaluated for associated or underlying organ involvement including pituitary, thyroid, and hepatic, or muscle (CPK) inflammation | |

| Cardiac * | Management/Next Dose for BMS-936558 (Nivolumab) + Ipilimumab Cardiac Toxicities |
|-------------------------------------|---|
| ≤ Grade 1 | Hold dose pending evaluation and observation.** Evaluate for signs and symptoms of CHF, ischemia, arrhythmia or myositis. Obtain history EKG, CK (for concomitant myositis), CK-MB. Repeat troponin, CK and EKG 2-3 days. If troponin and labs normalize may resume therapy. If labs worsen or symptoms develop then treat as below. Hold pending evaluation. |
| Grade ≥2 with suspected myocarditis | Hold dose.** Admit to hospital. Cardiology consult. Rule out MI and other causes of cardiac disease. Cardiac Monitoring. Cardiac Echo. Consider cardiac MRI and cardiac biopsy. Initiate high dose methylprednisolone. If no improvement within 24 hours, add either infliximab, ATG or tacrolimus. Consult algorithm for more details. Resume therapy if there is a return to baseline and myocarditis is excluded or considered unlikely. |
| Grade ≥2 with confirmed myocarditis | Off protocol therapy. Admit to CCU (consider transfer to nearest Cardiac Transplant Unit). Treat as above. Consider high dose methylprednisolone. Add ATG or tacrolimus if no improvement. Off treatment. |
| | |

*Including CHF, LV systolic dysfunction, Myocarditis, CPK, and troponin

**Patients with evidence of myositis without myocarditis may be treated according as “other event”

Note: The optimal treatment regimen for immune mediated myocarditis has not been established. Since this toxicity has caused patient deaths, an aggressive approach is recommended.

| Neurologic events | Management/Next Dose for Nivolumab and combination Nivolumab/ipilimumab |
|--|--|
| ≤ Grade 1 | Hold dose pending evaluation and observation. Resume with no change in dose when resolved to baseline at investigator discretion |
| Grade 2 | Hold dose pending evaluation and observation. Hold until ≤ Grade 1. Off protocol therapy if treatment with steroids is required. Resume at same dose level for peripheral isolated n. VII (Bell's palsy) |
| Grade 3 | Off protocol therapy |
| Grade 4 | Off protocol therapy |
| *Patients with any CNS events including aseptic meningitis, encephalitis, symptomatic hypophysitis, or myopathy, peripheral demyelinating neuropathy, cranial neuropathy (other than peripheral n. VII), GB syndrome, myasthenia gravis should be off study. | |
| Recommended management: See Neurologic Adverse Event Management Algorithm | |

| Endocrine Hypophysitis Adrenal Insufficiency | Management/Next Dose for Nivolumab and combination Nivolumab/ipilimumab |
|---|---|
| ≤ Grade 1 | Asymptomatic TSH elevation*; continue at investigator discretion with evaluation of thyroid function. |
| Grade 2 | Hold until patients are on a stable replacement hormone regimen. If treated with steroids, patients must be stable off steroids for two weeks. Resume at same dose level. |
| Grade 3 | Off protocol therapy. |
| Grade 4 | Off protocol therapy |
| 
Note all patients with symptomatic pituitary enlargement, exclusive of hormone deficiency, but including severe headache or enlarged pituitary on MRI should be considered grade 3 events. Isolated thyroid or testosterone deficiency may be treated as grade 2 if there are no other associated deficiencies and adrenal function is monitored.
 
Please evaluate pituitary function before beginning steroid therapy or replacement therapy of any kind.
 
*Note patients with thyroiditis may be retreated on replacement therapy. Patients must be evaluated to rule out pituitary disease prior to initiating thyroid replacement.
 | |
| 
Recommended management: TSH, T3, and T4 will be collected at baseline. After baseline, TSH will be collected every 6 weeks; T3/T4 will be collected when indicated. See Endocrine Management Algorithm
 | |

| Renal | Management/Next Dose for Nivolumab and combination Nivolumab/ipilimumab |
|--|--|
| ≤ Grade 1 | Continue at same dose at investigator discretion |
| Grade 2 | Hold pending evaluation. Resume at same dose level at investigator discretion. |
| Grade 3 | Off study treatment |
| Grade 4 | Off study treatment |
| 
Patients with fever should be evaluated as clinically appropriate. Patients may experience isolated fever during infusion reactions or up to several days after infusion. Evaluation over the course of 1-2 weeks should be done for other autoimmune events that may present as fever
 | |
| Infusion reaction | Management/Next Dose for Nivolumab and combination Nivolumab/ipilimumab |
| ≤ Grade 1 | Continue at slower rate at investigator discretion |
| Grade 2 | Hold until ≤ Grade 1. Resume at same dose level |
| Grade 3 | Hold until ≤ Grade 1. Resume at same dose level |
| Grade 4 | Off protocol therapy |
| 
Patients with fever should be evaluated as clinically appropriate. Patients may experience isolated fever during infusion reactions or up to several days after infusion. Evaluation over the course of 1-2 weeks should be done for other autoimmune events that may present as fever
 
See section 5.8- Treatment of Nivolumab or Ipilimumab Infusion reactions
 | |

| Fever | Management/Next Dose for Nivolumab |
|--------------|---|
| ≤ Grade 1 | Evaluate and continue at same dose level |

| Fever | Management/Next Dose for Nivolumab |
|--|--|
| Grade 2 | Continue at investigator discretion |
| Grade 3 | Hold until \leq Grade 1. Resume at same dose level at investigator discretion. |
| Grade 4 | Off protocol therapy |
| Patients with fever should be evaluated as clinically appropriate. Patients may experience isolated fever during infusion reactions or up to several days after infusion. Evaluation over the course of 1-2 weeks should be done for other autoimmune events that may present as fever | |
| See section 5.8: Treatment of Nivolumab or Ipilimumab Infusion reactions | |

If treatment is delayed >8 weeks for an adverse event, the patient must be permanently discontinued from study therapy.

Patients requiring high dose steroid treatment for autoimmune or inflammatory events should be managed as described in section 5.7, except for a short course of tapering steroids for infusion reaction, skin rash, or endocrine events.

Patients with grade 3 thyroiditis and skin rash may continue therapy as for grade 2 events with resolution and stable replacement treatment.

Patients with thyroiditis or hypopituitarism who are stable as above may be restarted with replacement hormones including thyroid hormone and physiologic doses of corticosteroids. Please note that grade for hypophysitis with symptoms of headache, visual, or neurologic changes or radiologic evidence of pituitary enlargement and other CNS events such as aseptic meningitis or encephalitis should be considered grade 3 events.

Any patient who requires additional immune suppressive treatment beyond steroids should go off protocol therapy.

Patients requiring $>$ two dose delays, other than for evaluation for the same event, should go off protocol therapy. Patients may be dose-delayed for evaluation and restarted depending on results.

Prior to starting corticosteroids or hormone replacement for any reason, appropriate endocrine testing including cortisol, ACTH, TSH and T4 must be obtained to document baseline.

Please note that in some cases the treatment algorithms recommend steroids if symptoms do not resolve in 7 days. However, this recommendation is not meant to delay steroid treatment at any time it is clinically indicated.

Any patient started on corticosteroids initially who is determined to not require steroids treatment for an autoimmune adverse event may resume therapy after a 2 week observation period without further symptoms at the discretion of the PI or investigator.

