5.4 Duration of Therapy

In the absence of treatment delays due to adverse event(s), treatment may continue for up to 46 doses in Cohort A or until one of the following criteria applies. In Cohort B, treatment may continue for up to 4 doses of combination therapy (nivolumab + ipilimumab), and up to 46 doses of nivolumab monotherapy after the combination therapy, or until one of the following criteria applies:

- Disease progression, as per section 5.9
- Intercurrent illness that prevents further administration of treatment,
- Any patients who require additional immune suppressive treatment beyond steroids should go off study treatment
- Unacceptable adverse event(s) which include the following (see also section 6 and

specific algorithms in Appendix E):

- Any grade 2 drug-related uveitis or eye pain or blurred vision that does not respond to topical therapy and does not improve to Grade 1 severity within the re-treatment period OR requires systemic treatment
- Patients requiring > two dose delays for the same type of event should go off protocol therapy.
- Any adverse event, laboratory abnormality, or intercurrent illness which, in the judgment of the investigator, presents a substantial clinical risk to the subject with continued study drug dosing
- Any dosing interruption lasting >6 weeks, with the following exceptions:
- Patients being tapered after high dose corticosteroids over one month followed by a two-week observation period will be allowed an additional two weeks to restart treatment (a maximum eight week interruption).
- Dosing interruptions >6 weeks that occur for non-drug-related reasons may be allowed if approved by the Investigator. Prior to re-initiating treatment in a subject with a dosing interruption lasting >6 weeks, the Principal Investigator must be consulted.
- Grade 3 drug-related autoimmune or inflammatory events including uveitis, pneumonitis, diarrhea, colitis, neurologic adverse events, hypersensitivity reaction, or infusion reaction of any duration requires discontinuation except as noted below:
- Any other grade 3 non-skin, drug-related AE lasting >7 days including fatigue.
- Any grade 3 or 4 drug-related laboratory abnormality or electrolyte abnormality, not associated with underlying organ pathology, that does not require treatment except for electrolyte replacements **does not** require treatment discontinuation.

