- Grade 3 amylase or lipase abnormalities that are not associated with diabetes mellitus (DM), associated liver or gall bladder inflammation clinical manifestations of pancreatitis and which decrease to \leq Grade 2 within 1 week of onset **may** resume study treatment when resolved.
- Any grade 4 events except as noted above.
- Patient decides to withdraw from the study, or
- General or specific changes in the patient's condition render the patient unacceptable for further treatment in the judgment of the investigator.

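### Section 5.4 and the Section 6 text give the laboratory-abnormality exemption different scopes, so an insulin-treated Grade 4 or prolonged Grade 3 abnormality meets a stopping rule in one but not the other

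*Combined protocol and SAP*

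**What the plan says.** Section 5.4 (Duration of Therapy) lists the adverse events that end treatment and the exceptions. Its exemption for Grade 3-4 drug-related laboratory or electrolyte abnormalities is limited to those "not associated with underlying organ pathology, that does not require treatment except for electrolyte replacements". Two of its stopping criteria catch what falls outside the exceptions: "Any other grade 3 non-skin, drug-related AE lasting >7 days including fatigue" and "Any grade 4 events except as noted above".

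The Section 6 text (Dosing Delays/Dose Modifications) exempts the same class of event at the same grades, but the permitted management is wider: "that can be managed independently from underlying organ pathology with electrolyte replacement, hormone replacement, insulin, or that does not require treatment".

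The pancreatitis amylase/lipase table in Section 6 adds, in its Grade 3 and Grade 4 rows only: "Patients who develop symptomatic pancreatitis or DM should be taken off treatment". Section 5.4 likewise withholds its own Grade 3 amylase/lipase exception when the enzyme rise is associated with diabetes.

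Section 5.4 refers the reader to Section 6. The Section 6 table for other immunologically mediated events refers the reader back to 5.4 for its Grade 3 exceptions.

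**The concern.** The two exemption sentences concern the same events at the same grades and reach the same outcome, so they should have the same scope. They do not. Electrolyte replacement is the only treatment allowed under 5.4, while Section 6 also names hormone replacement and insulin.

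A site working from 5.4 and a site working from the Section 6 text could therefore handle the same laboratory event in opposite ways, one ending protocol therapy and the other continuing it. In a small two-stage trial of two immune checkpoint inhibitors, the stopping rule for a high-grade drug-related abnormality should not depend on which section the investigator opens. Both agents' adverse event lists include hyperglycaemia, and Section 3.2.11 allows patients with type I diabetes to enrol, so the case is foreseeable.

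**Working it through.** The plan states no figure on this point and no arithmetic applies. The check runs the same cases through both exemption sentences.

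**Inputs**
- Section 5.4 exemption: Grade 3-4, drug-related, no associated organ pathology, no treatment other than electrolyte replacement.
- Section 5.4 stopping criteria outside the exceptions: any other Grade 3 non-skin drug-related event lasting more than 7 days; any Grade 4 event.
- Section 6 text exemption: Grade 3-4, drug-related, manageable independently of organ pathology with electrolytes, hormone replacement or insulin, or needing no treatment.

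| Case (drug-related laboratory abnormality) | Section 5.4 | Section 6 text | Agree? |
|---|---|---|---|
| Grade 4, managed with insulin, no organ pathology | Exemption not met (insulin is not electrolyte replacement); Grade 4 criterion met: stop | Exempt: discontinuation not required | No |
| Grade 3 lasting more than 7 days, managed with insulin, no organ pathology | Exemption not met; prolonged Grade 3 criterion met: stop | Exempt: discontinuation not required | No |
| Grade 3 lasting 7 days or less, managed with insulin, no organ pathology, not classed as autoimmune or inflammatory | Exemption not met, but the duration criterion is not met either | Exempt | No clash |
| Grade 3-4, electrolyte replacement only, no organ pathology | Exempt | Exempt | Yes |
| Grade 4 or prolonged Grade 3, managed with insulin, judged to reflect organ pathology | Exemption not met: stop | Exemption can be read as not met | Yes, on that reading |

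The clash is confined to the first two rows. Hormone replacement differs between the sentences in the same way. For thyroiditis, however, Section 5.7 and the closing text of Section 6 agree on continuing with stable replacement, so part of that difference is covered elsewhere. Neither passage covers insulin.

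**Does a cross-reference settle it?** Section 5.4 points to Section 6. The Grade 3 row of the immunologically mediated table points back to 5.4, and its Grade 4 row ends therapy with no exception, although the text that follows exempts some Grade 4 laboratory abnormalities. Neither section is given precedence.

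**Secondary point: the diabetes sentence.** Take a Grade 3-4 amylase or lipase rise with new diabetes treated with insulin. The table takes the patient off. Section 5.4 points the same way where the hyperglycaemia is Grade 4 or prolonged Grade 3: diabetes removes the enzyme exception and insulin removes the laboratory exemption. The Section 6 text gives a different answer only if the glucose abnormality is judged manageable independently of organ pathology. Nothing says where exempt insulin-treated hyperglycaemia ends and the diabetes rule begins.

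**The case against.** The strongest reply is that both exemptions carry an organ-pathology condition. If immune-mediated diabetes counts as organ pathology, the Section 6 exemption does not apply and the passages agree. That reply stands for those patients, but not for a laboratory abnormality managed with insulin and judged free of organ pathology.

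A second reply is that the Section 6 text only says discontinuation is not required. It does not oblige anyone to re-treat, and both sections let the investigator stop for any abnormality judged to carry serious risk. This softens the consequence, but discretion to stop under Section 6 does not remove the stopping criterion in 5.4.

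Third, Section 6 directs sites to the Appendix B algorithms, and the endocrinopathy figure is not reproduced in the text reviewed. The absence of a precedence rule is therefore established only for the visible text.

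A reader might also draw four stronger conclusions that the documents do not support:
- **That there are three competing rules.** For insulin-treated diabetes, 5.4 and the amylase/lipase table generally point the same way. The mismatch is between 5.4 and the Section 6 text.
- **That the table removes every patient who develops diabetes.** Its sentence sits only in the Grade 3-4 rows for enzyme elevation and may cover only diabetes arising with such a rise.
- **That the chance of a case can be computed from the adverse event lists.** The nivolumab list puts hyperglycaemia and diabetes with ketoacidosis below 3%, and the ipilimumab list puts hyperglycaemia at 20% or less. Neither gives a rate for Grade 3-4, insulin-treated events without organ pathology.
- **That the mismatch undermines the efficacy endpoints.** Section 13.4 already counts loss to follow-up or death within 6 months as failure, and Section 13.6.2 keeps all eligible patients in the response analysis. Any effect of stopping on follow-up is common to all toxicity stops.

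**Conclusion.** The inconsistency is real and narrow. For a drug-related laboratory abnormality managed with insulin and without organ pathology, at Grade 4 or at Grade 3 lasting more than 7 days, Section 5.4 supplies a stopping criterion and the Section 6 text says discontinuation is not required. No visible passage decides between them. The relation to the diabetes sentence in the amylase/lipase table is a lesser ambiguity.

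The number of patients affected cannot be estimated from the documents. The conclusion rests on the plain wording of the two exemptions and on the assumption that the unseen endocrinopathy figure does not settle the matter. It should be corrected because it concerns when treatment stops for a high-grade drug-related event. It does not call the sample size or the efficacy analysis into question, and this review takes no position on which rule is clinically right.

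**What to change.** Reconcile the passages in the next amendment:
- Use one identical list in Section 5.4 and the Section 6 text of the managed laboratory abnormalities that are exempt from discontinuation, saying explicitly whether hormone replacement and insulin are included and keeping one wording of the organ-pathology condition.
- State in both places how that list relates to the diabetes sentence in the amylase/lipase table, including whether that sentence applies only when an enzyme rise is present.
- Align the Grade 4 row of the immunologically mediated table with the result, and check the Appendix B endocrinopathy algorithm against it.

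The clinical team decides which rule applies. The cost is a wording amendment and notice to sites, with no extra patients, data or analyses.
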